8.4.1 Time Period and Frequency for Collecting AE and SAE Information

Immediate Post-vaccination Observation Period

All participants will be kept under observation for 30 minutes after each vaccination to ensure their safety. The post-vaccination observation should be documented in the source document.

Reactogenicity

Solicited injection site reactions will be collected from the day of vaccination (D01) until 7 days after each vaccination (D01 + 7 days).

Solicited systemic reactions will be collected from the day of vaccination (D01) until 7 days after each vaccination (D01 + 7 days).

The solicited injection site reactions and systemic reactions that are pre-listed in the DCs and CRF, together with the intensity scales, are presented in [Appendix 10.3.5.1.1](#).

Unsolicited Adverse Events

Unsolicited AEs include unsolicited non-serious AEs and SAEs. The intensity grading scale for unsolicited non-serious adverse events is presented in [Appendix 10.3.5.1.2](#).

Unsolicited non-serious AEs will be collected from the day of vaccination (D01) until 21 days after the last vaccination (D01 + 21 days).

SAEs will be collected and assessed throughout the study, from inclusion until 12 months after the last vaccination up to D366 (Supplemental Cohorts 1 and 2 Booster Arms) or D387 (Original

Phase II Cohort and Supplemental Cohorts Comparator Group). However, before the first study intervention administration, only SAEs related to study procedures are to be collected in the CRF (eg, SAEs related to blood sampling).

All SAEs will be recorded and reported to the Sponsor or designee immediately and under no circumstance should this exceed 24 hours, as indicated in [Appendix 10.3](#). The Investigator will submit any updated SAE data to the Sponsor within 24 hours of it being available.

Investigators are not obligated to actively seek information on AEs or SAEs after conclusion of the study participation. However, if the Investigator learns of any SAE, including a death, at any time after a participant has been discharged from the study, and he/she considers the event to be reasonably related to the study intervention or study participation, the Investigator must promptly notify the Sponsor.

Medically-Attended Adverse Events (MAAEs)

MAAEs will be collected throughout the study.

Adverse Events of Special Interest (AESIs)

AESIs will be collected throughout the study.

See [Section 8.4.6](#) for the list of AESIs.

8.4.2 Method of Detecting AEs and SAEs

Individual DCs, specifically designed for this study by the Sponsor and provided to the study sites, will be given to study participants for the recording of daily safety information. These DCs will include pre-listed terms and intensity scales as well as areas for free text to capture additional safety information or other relevant details. Participants will also be provided with rulers for measuring the size of injection site reactions, and with standard digital thermometers for measuring daily temperatures. To ensure consistency of reporting, the study sites will instruct participants on how to correctly use these tools.

At specified intervals, the Investigator or a designee will interview the participants to collect the information recorded in the DC and will attempt to clarify anything that is incomplete or unclear. All clinical study information gathered by the study site will be reported electronically by the Investigator or authorized designee using a web-based CRF. Any information that was not documented in the DC will first be captured in the source document and then reported electronically.

The 12-month (post-last injection) follow-up will be done by interviewing participants at Visit 7 (Supplemental Cohorts 1 and 2 Booster Arms) or Visit 8 (Original Phase II Cohort and Supplemental Cohorts Comparator Group) (or over the telephone if the visit cannot be performed in-person) using a questionnaire to capture SAEs and AESIs, if applicable.

Care will be taken not to introduce bias when detecting AEs and/or SAEs. Open-ended and non-leading verbal questioning of the participant is the preferred method to inquire about AE occurrences.

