†††† All participants will be scheduled to attend V06 for blood sampling and 12-Month (post-VAC) Safety Follow-up. However, if any participants discontinue the study early, they are still to be followed for safety and are to be contacted with a Safety Follow-up call to identify the occurrence of any SAEs and AESIs that had not yet been reported. If discontinuation occurs at a scheduled visit, the participant will be provided a Memory Aid instead of a DC for SAE follow-up (including AESIs) until the Safety Follow-up call. If a participant discontinues between visits (with no Memory Aid provided yet), the participant will use the last DC received to collect information for the Safety Follow-up call. For participants who have prematurely terminated the study, the site should attempt to contact them and complete this 12-month safety follow-up (and all other scheduled safety follow-ups), except if they specified that they do not want to be contacted again and it is documented in the source document.

Table 1.3: Schedule of Activities for Supplemental Cohorts Comparator Group

Phase II/III Study, 8 Visits, 3 Telephone Calls, 2 Vaccinations, 8 Blood Sample Time points, Approximately 13 Months' Duration Per Participant

Visit (V) / Contact	Collection of information in the CRF	V01	TC1##	V02	TC2##	V03	TC3##	V04	V05	V06	V07	V08 or Safety Follow-up ####
Study timelines (Day [D])		D01	D09	D22	D30	D36	D43	D78	D134	D202	D292	D387
Time interval (days)			V01 +8 days	V01 +21 days	V02 +8 days	V02+14 days	V02+21 days	V02 +56 days	V02 +112 days	V02 +180 days	V02 +270 days	V02+365 days
Time windows (days)		N/A	[+2days]	[+3 days]	[+2 days]	[+3 days]	[+2 days]	[+9 days]	[+14 days]	[+21 days]	[+21 days]	[+21 days]
Visit procedures:												
Informed consent	X	X										
SARS-CoV-2 rapid serodiagnostic test	X	X										
Inclusion/exclusion criteria	X	X										
Collection of demographic data	X	X										
Collection of significant medical history including high risk medical conditions	X	X										
Collection of risk factors for SARS-CoV-2 exposure and COVID-19	X	X										
Physical examination*		X										

Visit (V) / Contact	Collection of information in the CRF	V01	TC1‡‡	V02	TC2‡‡	V03	TC3‡‡	V04	V05	V06	V07	V08 or Safety Follow-up ****
Study timelines (Day [D])		D01	D09	D22	D30	D36	D43	D78	D134	D202	D292	D387

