2.3.3 Overall Benefit-Risk Conclusion

Considering the significant medical need, scale of the pandemic, urgent requirement for measures to address the pandemic, together with actions taken to minimize risk to participants enrolled in the study, there is no unreasonable and significant risk of illness or injury for the participants.

3 Objectives and Endpoints

The study objectives and the corresponding endpoints are described in [Table 3.1](#).

Table 3.1: Objectives and endpoints

Primary Safety (applicable to Original Phase II Cohort as well as Supplemental Phase III Cohorts)	
To assess the safety profile of all participants in each age group and in each study Intervention Group.	
 • Presence of unsolicited systemic AEs reported in the 30 minutes after each vaccination • Presence of solicited (pre-listed in the participant's diary card [DC] and [electronic] Case Report Form [CRF]) injection site reactions and systemic reactions occurring up to 7 days after each vaccination • Presence of unsolicited AEs reported up to 21 days after the last vaccination • Presence of serious adverse events (SAEs) throughout the study • Presence of AESIs throughout the study • Presence of MAAEs throughout the study
Primary Immunogenicity-Original Phase II Cohort	
To assess the neutralizing antibody profile 14 days after the last vaccination (D36) in SARS-CoV-2-naïve adults in each study Intervention Group.	
Neutralizing antibody titers will be measured in SARS-CoV-2-naïve participants for each study Intervention Group against the D614G variant.
 
 • Individual serum neutralizing titer at D01 and D36 • Individual serum neutralization titer fold-rise post-vaccination relative to D01 at D36 • 2-fold-rise and 4-fold-rise in serum neutralization titer [post/pre] (fold-rise ≥ 2 and ≥ 4) at D36 relative to D01 • Responders in SARS-CoV-2 naïve, defined as participants who had baseline values below lower limit of quantification (LLOQ) with quantifiable neutralization titer above assay LLOQ at D36
Primary Immunogenicity-Supplemental Cohort 1	

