8.4.7 Medically-Attended Adverse Events

MAAEs will be collected using the same process as other AEs. See [Appendix 10.3.1](#) for definition of MAAEs.

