9.4.2.2.2 Primary - Safety

The main parameter will be described for all safety endpoints. The percentage of participants (using as denominator the number of participants) will be provided for analysis of solicited AEs, unsolicited AEs (including immediate systemic AEs within 30 minutes), SAEs, AESIs and MAAEs. The corresponding 95% CIs for the percentages will be calculated based on the Clopper-Pearson method. In the priming vaccine groups (comparator for Cohorts 1 and 2), subgroup analyses will be performed by age group (18-55 years old and \geq 56 years old), high-risk medical conditions group, and baseline SARS-CoV-2 naïve status for the main safety analyses. In the Booster Groups (in Cohorts 1 and 2), subgroup analyses will be performed by age group (18-55 years old and \geq 56 years old), high-risk medical conditions group, priming vaccine platform, and individual priming vaccine. Safety endpoints will be analyzed for each of the CoV2 preS dTM primary series dosages administered in the Original Phase II Cohort (ie, 5-10-15 μ g). The SafAS population will be used for safety analyses for the following endpoints:

- Presence and relationship of unsolicited (immediate) systemic AEs reported in the 30 minutes after each vaccination.
- Presence, time of onset, number of days of occurrence, intensity, action taken, and whether the reaction led to early termination from the study, of solicited (pre-listed in the participant's DC and CRF) injection site reactions and systemic reactions occurring up to 7 days after each vaccination.
- Presence, nature (MedDRA SOC and PT), time of onset, duration, intensity, relationship to vaccination, and whether the event led to early termination from the study of unsolicited AEs reported up to 21 days after the last vaccination.
- Presence, nature (MedDRA SOC and PT), time of onset, seriousness criteria, relationship to vaccination, outcome, and whether the event led to early termination from the study, of SAEs.
- Presence, nature (MedDRA SOC and PT), relationship to vaccination of all protocol-specified AESIs from the time of the first study vaccination throughout the study.
- Presence, nature (MedDRA SOC and PT), relationship to vaccination of MAAEs throughout the study.

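### The 12-month questionnaire, the early-discontinuation call and the Memory Aid omit MAAEs, a whole-study primary safety endpoint, so no MAAE prompt is specified after discontinuation

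*Protocol*

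**What the plan says.** **Endpoint.** Table 3.1 (Primary Safety, applicable to the Original Phase II Cohort and the Supplemental Cohorts) lists "Presence of MAAEs throughout the study" beside SAEs and AESIs, with the same whole-study period. Section 8.4.1 repeats it: "MAAEs will be collected throughout the study". Section 8.4.7 adds: "MAAEs will be collected using the same process as other AEs".

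**Analysis.** Section 9.4.2.2.2, on the Safety Analysis Set, covers MAAEs in this sentence: "The percentage of participants (using as denominator the number of participants) will be provided". Section 9.4.2.1.1 does the same for the Original Phase II Cohort.

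**Final contact.** Section 8.4.2 describes the 12-month interview, in person or by telephone, as done "using a questionnaire to capture SAEs and AESIs, if applicable".

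**Early discontinuation.** According to the footnotes to Tables 1.1 to 1.3 and Section 7.2, participants who discontinue early "are to be contacted with a Safety Follow-up call to identify the occurrence of any SAEs and AESIs that had not yet been reported". For anyone stopping on a visit day, the text reads: "the participant will be provided a Memory Aid instead of a DC for SAE follow-up (including AESIs) until the Safety Follow-up call". Those who stop between visits, and so have no Memory Aid, use the last diary card they received.

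**Diary cards.** In the booster arms (Table 1.2), DC3 records MAAEs from V04 (D91) to V06 (D366). In the Original Phase II Cohort and the Comparator Group (Tables 1.1 and 1.3), DC3 runs from V04 (D78) to V08 (D387). The footnotes there say MAEs, an undefined term that can only sensibly mean MAAEs. In all three schedules DC3 is collected by interview at the last visit, and the row for SAEs, MAAEs and AESIs makes them reportable at any time.

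**The concern.** SAEs, AESIs and MAAEs share one collection period and one analysis paragraph, but only the first two appear in the instruments used at the end of follow-up and after discontinuation. A site that follows the text literally would ask an early discontinuer about SAEs and AESIs and would not ask about a non-serious medically-attended event.

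No other route fills the gap. Section 8.4.7 ties MAAEs to the general AE process, but under Section 8.4.1 non-serious unsolicited AEs are collected only until 21 days after the last vaccination. Beyond that, a non-serious MAAE that is not an AESI depends on the diary card or on the participant volunteering it.

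Because the summary is a percentage of participants and not a rate per unit of follow-up, someone whose MAAE ascertainment stops early still counts in full in the denominator. A reported MAAE percentage could therefore be somewhat low, and a reader of the results would not see that MAAE follow-up was shorter than SAE and AESI follow-up for the same people.

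**Working it through.** No sample-size, power or alpha figure bears on this, so the check compares the text by participant status.

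**1. Participants who stay in the study.** Planned diary coverage of MAAEs:

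| Group | DC1 | DC2 | DC3 |
|---|---|---|---|
| Booster arms (Table 1.2) | D01 to V03 (D29) | V03 to V04 (D91) | V04 to V06 (D366) |
| Original Phase II Cohort and Comparator Group (Tables 1.1, 1.3) | D01 to V02 (D22) | V02 to V04 (D78) | V04 to V08 (D387) |

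Coverage is continuous to the last visit, where DC3 is collected by interview. The Section 8.4.2 questionnaire adds to this route and does not replace it. What is missing is a direct MAAE question on the final form. This matters most if the contact is by telephone, since the questionnaire is the only instrument that Section 8.4.2 names for the 12-month contact.

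**2. Discontinuation at a scheduled visit.** The diary card, which has MAAE fields, gives way to a Memory Aid described for SAEs including AESIs. The later call has the same scope. No MAAE tool and no MAAE prompt are specified.

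**3. Discontinuation between visits.** The last diary card is kept, and it has MAAE fields. The call's stated purpose is still SAEs and AESIs not yet reported. A tool exists, but there is no matching question.

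**4. Does the instruction to complete all scheduled safety follow-ups rescue cases 2 and 3?** No. Section 7.2 tells sites to attempt these contacts, but the 12-month contact it refers to is itself defined by SAEs and AESIs. Participants lost to follow-up are outside this point, because Section 7.2 says no further safety information will be sought from them.

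**5. Denominator.** Sections 9.4.2.1.1 and 9.4.2.2.2 use the number of participants, so those in cases 2 and 3 remain in it.

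**6. Size.** Each discontinuer can add at most one missed participant to the numerator, so the shortfall from cases 2 and 3 cannot exceed the proportion of a group that discontinues early. The protocol gives no such proportion at 12 months, overall or by arm, so the bound cannot be given a number.

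**The case against.** The strongest reply has four parts.

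- **Completers are covered.** DC3, the any-time reporting row and the open-ended questioning in Section 8.4.2 all support MAAE capture to the last visit. This stands. A reader might infer that MAAE capture falls off late in follow-up for everyone; the documents do not support that.

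- **Withdrawal ends the study for that person.** Section 7.2 says a withdrawn participant is discontinued from the study, and Section 8.4.1 does not oblige investigators to seek AEs actively once participation is over. Whole-study MAAE collection could then end at withdrawal, and limiting later contact to SAEs and AESIs would be a defensible choice. This stands in part: it is a possible reading, but the protocol never states it. It follows the same people to 12 months for two events with an identical collection period.

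- **No between-arm bias is shown.** A reader might contrast the time from the penultimate to the last visit: 366 − 181 = 185 of 365 days (51%) in booster arms against 387 − 292 = 95 of 386 days (25%) in the Comparator Group. Those figures measure visit spacing, and DC3 covers both intervals. The intermediate DC3 review is only a reminder and a chance to ask questions, so collection falls at the last visit everywhere: D91 to D366 is 275/365 = 75%, and D78 to D387 is 309/386 = 80%. The apparent asymmetry largely disappears. MAAEs are also summarised descriptively, with no between-group test, and the Comparator Group is non-randomised.

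- **The attrition figures do not apply.** A reader might take the 10%, 3% and 15% in Section 9.2 as discontinuation rates. The 10% and 3% are planning assumptions for reaching D36 and D15. The 15% allows for uptake of authorised vaccines, and those participants stay in follow-up. This objection stands in full.

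**Conclusion.** The mismatch is real and worth correcting, but narrow. The 12-month questionnaire, the discontinuation call and the Memory Aid do not match a primary safety endpoint that includes MAAEs for the whole study. For participants who remain, the defect is a missing structured prompt. For those who discontinue at a visit, MAAE solicitation is not specified at all. For those who discontinue between visits, a diary card with MAAE space exists but the call does not ask about it.

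It would be an overstatement to say that MAAE capture is nil after discontinuation: between-visit discontinuers keep a card with MAAE fields, and spontaneous reports are possible. What stops is specified active solicitation.

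The direction of any effect is towards under-reporting. Its size cannot be given from the protocol. The conclusion assumes that the questionnaire, call and Memory Aid contain what the protocol says and no more; the forms themselves are not part of the document.

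**What to change.** Choose one of two changes and apply it throughout.

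1. **Preferred:** add MAAEs to the 12-month questionnaire in Section 8.4.2 (including the telephone version), to the Safety Follow-up call and to the Memory Aid. Carry the wording into Section 7.2 and the footnotes to Tables 1.1 to 1.3.
2. **Otherwise:** state in the Table 3.1 endpoint and in Section 8.4.1 that MAAE ascertainment ends at discontinuation, so that the shorter period is explicit when percentages are read.

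The first option costs one added item on existing forms and calls, with no new visit or sample. The second costs a sentence.

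Two small corrections belong in the same edit. The DC3 footnotes to Tables 1.1 and 1.3 should say MAAEs. Sections 8.4.2 and 7.2 place the booster-arm 12-month contact at Visit 7, whereas Table 1.2 ends at V06 (D366), and these should be reconciled.

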8.4.3 Follow-up of AEs and SAEs

After the initial AE/SAE report, the Investigator is required to proactively follow each participant at subsequent visits/contacts, unless a participant refuses further contact.

All AEs that are considered by the Investigator as serious, or to be related to the study intervention administered or that led to study or vaccination discontinuation, will be followed during the conduct of the study until resolution, stabilization, or the participant is lost to follow-up (as defined in [Section 7.3](#)). For related SAEs ongoing at last study visit, such follow-up may need to continue after the end of the study. Further information on follow-up procedures is provided in [Appendix 10.3](#)

8.4.4 Regulatory Reporting Requirements for SAEs

- Prompt notification by the Investigator to the Sponsor of an SAE is essential so that legal obligations and ethical responsibilities towards the safety of participants and the safety of a study intervention under clinical investigation are met.
- The Sponsor has a legal responsibility to notify both the local regulatory authority and other regulatory agencies about the safety of a study intervention under clinical investigation. The Sponsor will comply with country-specific regulatory requirements relating to safety reporting to the regulatory authority, IRB / IEC, and Investigators.
- Investigator safety reports must be prepared for SUSAR according to local regulatory requirements and Sponsor policy and forwarded to Investigators as necessary.
- An Investigator who receives an Investigator safety report describing a SAE or other specific safety information (eg, summary or listing of SAEs) from the Sponsor will review and then file it and will notify the IRB/IEC, if appropriate according to local requirements.
- Investigator safety reports must be prepared for SUSARs according to local regulatory requirements and Sponsor policy and forwarded to Investigators as necessary.

8.4.5 Pregnancy

Pregnant women are not eligible to participate in the study and females of childbearing potential agree to use an effective contraceptive method during a period starting 4 weeks prior to the first vaccination and ending 12 weeks after the last vaccination, as defined in the inclusion criteria. However, a participant could potentially become pregnant during her participation.

If the pregnancy starts during the period of contraception or abstinence:

- Details of all pregnancies in female participants will be collected after the start of study intervention and until the pregnancy outcome.
- When pregnancy is reported, the Investigator should promptly inform the Sponsor and will record pregnancy information together with the contraceptive method on the appropriate form and submit it to the Sponsor no later than 1 month of learning of the pregnancy.
- While pregnancy itself is not considered to be an AE or SAE, any pregnancy complication or elective termination of a pregnancy for medical reasons will be reported as an AE or SAE.

- Abnormal pregnancy outcomes (eg, spontaneous abortion, fetal death, stillbirth, congenital anomalies, ectopic pregnancy), any serious event experienced by the pregnant women or by the newborn are considered SAEs and will be reported as such.
- The participant will be followed till the outcome of the pregnancy and the pregnancy outcome reported. The Investigator will collect follow-up information on the participant and the neonate, and the information will be forwarded to the Sponsor. Any termination of pregnancy will be reported, regardless of fetal status (presence or absence of anomalies) or indication for the procedure.
- The offspring will be followed for up to 12 months by the pharmacovigilance department. Any data collected after CRF lock will be transmitted to the pharmacovigilance department on the paper form.

If the pregnancy starts after the period of contraception or abstinence:

- The data collection will be the same during the period of the study. It will end at the last visit of the participant.
- The Investigator should promptly inform the Sponsor and will record pregnancy information together with the contraceptive method on the appropriate form and submit it to the Sponsor no later than 1 month of learning of the pregnancy. Pregnancy status will be collected, follow-up of the participant will continue as part of the study, but the participant will not be followed-up until the pregnancy outcome and the offspring will not be followed.
- Any post-study pregnancy-related SAE considered reasonably related to the study intervention by the Investigator will be reported to the Sponsor as described in [Section 8.4.4](#). While the Investigator is not obligated to actively seek this information in former study participants, he or she may learn of an SAE through spontaneous reporting.
- Any female participant who becomes pregnant while participating in the study will discontinue study intervention until delivery or until delivery and end of lactation. However, the participant will be followed for safety assessment (and may be followed for immunogenicity assessment, if applicable).

